
Safety Evaluations
 <hr/> 
Statistical And Analytic Plan
	
N/A, this study imposes minimal risk.
 <hr/> 
A. Identification of Barriers: The top 2 conceptual themes within each section of the interview (attitudes regarding general clinical trials, attitudes regarding CCTs, and perception of the Hispanic/Latino community) and the top 3 higher-level, holistic themes across the sections will be reported in terms of percentage of participants.
 
B. Assessment of the potential impact of the educational videos in Spanish on CRC knowledge: Use of repeated measures ANOVA with appropriate follow-up contrasts to compare total number of correct responses within three time points (baseline vs post-video; baseline vs 30 +/- 7 days follow up; post-video vs 30 +/- 7 days follow-up) accounting for multiple observations within participants.
 
C. Exploration of the potential relationship between an increase in health knowledge of a specific cancer via educational videos in Spanish and willingness to participate in CCTs: Since questionnaires will be completed pre- and post-video, we will explore, in a preliminary fashion, the association between watching the video (X) and willingness to participate in CCTs (Y) using repeated-measures/mixed-effects logistic regression on the paired responses of participants. The mediating effect of Study Day 1 post-video health knowledge levels (M) on the relationship between X and Y (established in the preliminary step above) will be explored. Using a structural equation modeling approach, two mixed-effects generalized linear models will be carried out: one model uses both X and M to predict Y, while another uses only X to predict M. The two models will be compared and tested using the algorithm introduced by Imai and colleagues. The estimated average causal mediation effect (from X to Y, through M) will be tested using the bootstrapping method with 1,000 replications, and the proportion of the effect being mediated will be reported as the effect size. Lastly, in order to explore an adjusted approach, the same steps used for the mediation model will be replicated, while incorporating demographic variables as covariates.

--	---

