1.4 Relevant Literature and Data

Use of the Church-based Approach: Approximately 75% of Foreign- and 55% of US-born Latino identify as Christian, respectively⁹ and 74% of Latinos attend Church at least 1-2 times a month.¹⁰ As a testament to the important role that the Church plays in the Latino community, several interventions have been evaluated in the Church setting¹¹⁻²⁵ including: breast cancer prevention;^{16,17,19} diabetes mellitus;^{14,23,24} cancer screening promotion;^{13,15} physical exercise promotion;^{18,21} HIV stigma reduction;²⁰ stroke prevention;²² organ donation promotion;²⁵ and cardiovascular risk reduction.^{11,12} With the exception of a recent study limited to Latino men,²⁶ we are not aware of any Church-based educational interventions that have: 1) educated Latinos on CRC or 2) reported strategies for their recruitment and retention. We believe that our approach, if successful, may have broad applicability for the recruitment of other ethnic minority groups with high religious beliefs across a multitude of denominations (e.g. 68% of Asians attend Church at least 1-2/month¹⁰).

Education of the general population/non-cancer afflicted individuals: Most CCT educational interventions target individuals afflicted with the disease.²⁷⁻³³ While only a handful target the non-affected general population,³⁴⁻³⁷ this approach may be uniquely suited for recruitment of Latinos in CCTs since in the Latino community the decision to enroll in a CCT is likely to be multifactorial and heavily influenced by input from family members.³⁸ In fact, a core value of Latino culture is *familismo*: “the concept of a broad network of familial support that extends beyond the nuclear family”.³⁹ Since lack of family support may act as a barrier to Latino CCT participation,^{40,41} we believe that: (1) educating the general population and non-cancer afflicted Latino individuals and families will facilitate Latino CCT participation and (2) the Church setting, given the multiple familial generations attending mass, is a viable venue for educating the Latino general population.

Education on a specific cancer & willingness to participate in CCTs: Unlike other studies aimed at increasing willingness to participate in CCTs solely through general education about CCTs, our study focuses primarily on education on a specific cancer.^{27-37,42} Since education on CRC has been shown to

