increase willingness to participate in CRC screening,⁴³ we anticipate it could similarly increase willingness to participate in CCTs. This can be achieved by increasing awareness of CRC and its treatment options ultimately leading to improved decision-making.²⁷

Questionnaire: Knowledge on CRC and willingness to participate in CCTs will be assessed using 3 subscales from 2 CRC knowledge questionnaires previously validated in English. [name] and [name] from the Odum Institute combined the 3 subscales^{44–46} to form our Pilot Study Questionnaire. This Pilot Study Questionnaire has been translated into Spanish by Language Line Solutions, hired through the UNC Clinical Research Support Office (CRSO), and revised, using an iterative process with input from the LCRB, for linguistic and cultural relevance and accuracy. The resultant Pilot Study Questionnaire consists of 29 items that assess health knowledge levels and 1 that assesses willingness to participate in CCTs (30 total questions). General knowledge on CRC will be assessed using the prompted 9-item “Awareness of warning signs” (Yes/No) and the prompted 11-item “Awareness of risk factors” (5 point Likert agreement scale) subscales of the “Bowel/CRC Cancer Awareness Measure (Bowel/CRC CAM)”.⁴⁵ Specific knowledge on CRC screening will be assessed using the 9-item “Knowledge on CRC screening” (mixed types of response options) subscale from the CRC Screening Decision Quality Instrument (CRC-DQI).⁴⁶ Our outcome variable, *willingness to participate in CCTs*, will be assessed using a “Yes/No” item.^{28,36,42} Our Pilot Study Questionnaire is used in all three surveys, namely the *CRC Knowledge Survey; Post Video CRC Knowledge Survey and 30 Day Follow Up CRC Knowledge Survey*. Additionally, the *CRC Knowledge Survey*, administered pre-video, includes seventeen questions capturing demographic information (47 total questions), while the *30 Day Follow Up CRC Knowledge Survey* contains in addition to the pilot study Questionnaire, an open-ended question aimed at capturing barriers preventing Latinos from participating in CCTs (31 total questions).

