Video: Previous studies demonstrate the superiority of a video-based approach compared to other educational tools in terms of knowledge acquisition and acceptance within the Latino population.^{42,43,47,48} Based upon strong recommendation from the UNC’s Audio and Video Production Team, we contracted DWALT Media, which has filmed videos for UNC Medical Center and worked with local churches, for the production of our Spanish educational videos. Filming occurred at UNC Medical Center and included animations, figures and 3D models. The videos will educate the participants on CRC symptoms, risk factors, screening and CRC facts. In addition, the third video will contain some information regarding CCTs. Since Latinos consider physicians a trustworthy source of

medical information,⁴⁹ our PI, a member of the STM Latino community, will present some of the educational material.

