1.5 Secondary Objectives

1. Assess the impact that CRC educational videos in Spanish may have on participants' CRC knowledge.
2. Assess the potential relationship between an increase in health knowledge of a specific cancer via educational videos in Spanish and willingness to participate in CCTs.

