3.2 Intervention/Treatment procedures

Study Day 1: Consented participants come to STM Church. During *Study Day 1*, they will be asked to complete the *CRC Knowledge Survey*, watch three CRC educational videos in Spanish and subsequently complete the *Post Video CRC Knowledge Survey* in Spanish. Both surveys will be administered on paper form.

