4.3 Secondary Endpoints

The Secondary Endpoints of our study are to assess the association of:

1. Educational videos on knowledge of CRC symptoms.
2. Educational videos on knowledge of CRC risk factors.
3. Educational videos on knowledge on CRC screening and facts.
4. Watching the videos and willingness to participate in CCTs.

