Secondary Endpoint 3: Use of repeated measures ANOVA with appropriate follow-up contrasts to compare total number of correct responses within three time points (baseline vs post-video; baseline vs 30 +/- 7 days follow-up; post-video vs 30 +/- 7 days follow-up) accounting for multiple observations within participants. Knowledge of CRC screening and general facts will be assessed using nine questions from the “Colorectal Cancer Decision Quality Instrument (CRC-DQI)”. The overall score will range from 0 to 9 and it is anticipated that average scores will increase after the intervention. Higher scores imply greater knowledge of screening and facts.

Secondary Endpoint 4: Since questionnaires will be completed pre and post video, we will explore, in a preliminary fashion, the association between watching the video (X) and willingness to participate in CCTs (Y) using repeated-measures/mixed-effects logistic regression on the paired responses of participants. The mediating effect of *Study Day 1* post-video health knowledge levels (M) on the relationship between X and Y (established in the preliminary step above) will be explored. Using a structural equation modeling approach, two mixed-effects generalized linear models will be carried out: one model uses both X and M to predict Y, while another uses only X to predict M. The two

models will be compared and tested using the algorithm introduced by Imai and colleagues^{50,51} The estimated average causal mediation effect (from X to Y, through M) will be tested using the bootstrapping method with 1,000 replications, and the proportion of the effect being mediated will be reported as the effect size. Lastly, in order to explore an adjusted approach, the same steps used for the mediation model will be replicated, while incorporating demographic variables as covariates.

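### The planned average causal mediation effect does not identify a causal share for CRC knowledge; the trial content of the third video is one reason among several

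*Combined protocol and SAP*

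**What the plan says.** - **Objective.** Section 1.5: "Assess the potential relationship between an increase in health knowledge of a specific cancer via educational videos in Spanish and willingness to participate in CCTs". The matching endpoint in section 4.3 is "Watching the videos and willingness to participate in CCTs".
- **Exposure.** Section 1.4 (Video) lists CRC content and adds: "In addition, the third video will contain some information regarding CCTs". Section 3.2 has participants "watch three CRC educational videos in Spanish and subsequently complete the" post-video survey, so this content precedes the second measurement. Section 2.1 describes a single-arm study.
- **Measurement.** Section 1.4 (Questionnaire): the instrument "consists of 29 items that assess health knowledge levels and 1 that assesses willingness to participate in CCTs (30 total questions"). The 29 items are three CRC subscales. The other questions are demographics at baseline and one open-ended question on barriers at 30 days.
- **Analysis.** Section 4.4, Secondary Endpoint 4: "one model uses both X and M to predict Y, while another uses only X to predict M". Then: "The estimated average causal mediation effect (from X to Y, through M) will be tested using the bootstrapping method with 1,000 replications". The proportion mediated is the effect size, and a second version adds demographic covariates. No other adjustment, identifying assumption or sensitivity analysis is stated.
- **Interpretation.** Section 1.4 says "our study focuses primarily on education on a specific cancer". Section 11 plans to publish the mediating effect of increased CRC knowledge.

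**The concern.** A mediated effect is causal only if, given X (viewing) and the covariates, nothing unmeasured drives both M (CRC knowledge) and Y (willingness). The plan adjusts for demographics at most. Attention, health literacy or prior interest in health could plausibly raise both.

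Two design features add to this. X is simply before versus after, so its effects on M and Y include time and answering the same questionnaire twice. And the videos may also change understanding of trials, which bears directly on willingness and is not measured. If that understanding moves with CRC knowledge, M stands in for it and part of its effect is credited to CRC knowledge.

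At stake is what the trial may say on its third objective. The share is the planned headline number for the idea that teaching about one cancer makes people more willing to join trials.

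**Working it through.** **Step 1. The plan's own figures.** Section 4.5 gives n = 60, a difference of 0.4, a pre-post correlation of 0.5 and power over 80%. Reading 0.4 in SD units, the SD of the paired difference is sqrt(2 x (1 - 0.5)) = 1, and the noncentrality is 0.4 x sqrt(60) = 3.10. A paired t-test at two-sided 5% (assumed; no alpha is stated) has 86.2% power. The figure reproduces, but concerns a mean change, not mediation. The item counts also reproduce: 9 + 11 + 9 = 29; 29 + 1 = 30; 30 + 17 = 47; 30 + 1 = 31. No question is left for trial understanding. The survey forms are not in the text, so this rests on the description in section 1.4.

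**Step 2. What the models estimate.** Let T be trial understanding. M and T have SD 1; X raises them by a and g; their correlation given X is r; their true effects on the log-odds of Y are bM and bT. If T is omitted, the fitted coefficient of M is, to first order, bM + bT x r. Hence

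- reported share ≈ a(bM + bT r) / (a bM + g bT)
- true share = a bM / (a bM + g bT)

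With bM = 0 the true share is 0 and the reported share is about r x a/g. With a = g = 0.4 that is 0% at r = 0 and 50% at r = 0.5. A simulation of the two models without random effects (400,000 participants, bT = 0.8) gave 0, 25, 50 and 75% at r = 0, 0.25, 0.5 and 0.75. With bM = 0.4 the true share is 33%, and it reported 33, 50, 67 and 83%.

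**Step 3. With the planned random intercept.** Only the gain of 0.4 and correlation of 0.5 for M come from section 4.5. Everything for T is assumed: gain 0.4 SD, pre-post correlation 0.5, log-odds 1.5 per SD (odds ratio about 4.5). Also assumed: intercept -0.3, person effect SD 1, no CRC-knowledge effect. M is taken at both Study Day 1 surveys, since a model of M on X needs both. Results from 3 x 100,000 participants, mediated effect in percentage points:

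| r | Only gains correlated: effect, share | Baseline levels too: effect, share |
|---|---|---|
| 0.3 | 1.7, 17% | 2.9, 30% |
| 0.5 | 2.7, 29% | 4.8, 49% |
| 0.7 | 3.8, 41% | 6.7, 69% |

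At r = 0 the share is about 0%. Repeat simulations at r = 0.5 gave 27 to 31% and 47 to 52%. If T instead gains 0.8 SD, the shares at r = 0.5 are 14% and 25%; if 0.2 SD, 59% and 100%.

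**Step 4. Source and direction.** With T unchanged by the videos and correlated with M at baseline only, a false mediated effect of 1.7, 3.0 and 4.3 points remains at r = 0.3, 0.5 and 0.7, against 2.9, 4.8 and 6.7 above: roughly 60%. This split depends on the assumptions. In other runs the false effect stayed near 4.7 points whatever the mean gain in T, because it follows correlated variation and not the mean shift. With opposite signs (bM = 1.0, bT = -0.5) the mediated effect falls from 7.0 points at r = 0 to 5.9 (gains only) or 4.9 (baseline too) at r = 0.7, a downward bias.

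**Step 5. At n = 60.** With r = 0.5 and baseline correlation, the 5-95% range of the estimated share is about -189% to 215%.

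**Step 6. A sensitivity grid.** In one simulated data set (coefficient of M 0.65), subtract d from that coefficient:

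| d | 0 | 0.16 | 0.32 | 0.48 | 0.65 |
|---|---|---|---|---|---|
| Share, total effect held fixed | 50% | 38% | 25% | 13% | 0% |

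In a similar run with the total recomputed at each d, the shares were 49, 42, 33, 20 and 0%, so the convention must be stated. The shift between the unadjusted and demographic-adjusted models is not a safe benchmark for d. In the gains-only case at r = 0.5, where the true coefficient is 0, adjusting perfectly for the stable parts (an extreme case) moved it from 0.38 to 0.64, away from the truth.

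**The case against.** **The plan is already cautious.** It calls the analysis preliminary and exploratory, the objective concerns a potential relationship, and this is the last of four secondary endpoints beside a qualitative primary one. That stands and limits the seriousness. It does not identify the effect: a causal quantity is still tested and a share still reported as effect size.

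**The trial segment is not the cause.** A reader might infer that the content of the third video by itself invalidates the mediation analysis, or that it inflates the share. The documents support neither. With no correlation there is no bias from this pathway, with opposite signs the bias is downward, and without the segment the share would still be unidentified. This objection stands in full.

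**Section 1.4 does not contradict itself.** Its contrast is with studies relying only on general trial education, and it claims a primary, not exclusive, focus on one cancer. Some trial content is compatible with that and is disclosed.

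**The package reading is largely in place.** X is watching the video, and sections 1.2, 4.3 and 5 refer to the videos or intervention as a whole. What is missing is a statement, where results are interpreted, that the package includes trial information.

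**The simulation inputs are generous.** A log-odds of 1.5 per SD is large for a short segment. Halving it lowers the mediated effect, but the share changes less (27% and 56% at r = 0.5 in one smaller run), because bT cancels in r x a/g. The percentages remain illustrations.

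**Noise would dominate at n = 60.** True, and a further reason not to present the share as a causal effect size.

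**Conclusion.** The concern holds as one of unmeasured mediator-outcome confounding in a single-arm before-after design, with trial understanding as an added, unmeasured possible pathway. The planned mediated effect and share cannot be read as the causal contribution of CRC knowledge. Nothing in the documents supports a zero correlation between trial understanding and CRC knowledge, and no planned item can check it.

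The actual bias is unknown in size and sign. The figures of about 0% at r = 0 and roughly 27 to 50% at r = 0.5 assume no true CRC-knowledge effect, equal gains of 0.4 SD and invented values for trial understanding. They show that a sizeable share can appear with nothing behind it, not that it will.

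A reader might also infer that secondary endpoint 4 as a whole fails. It does not. As an association of the whole video package with willingness it is untouched by the second pathway, though it remains a before-after contrast.

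**What to change.** 1. **Wording.** In the Synopsis (Statistical and Analytic Plan, part C), section 4.4 (Secondary Endpoint 4) and section 11, report the mediation result as an exploratory association between CRC knowledge and willingness, not as a causal mediation effect. State that the videos include trial information, that trial understanding was not measured, and that X cannot be separated from time or repeat testing.
2. **Sensitivity analysis with the same two models.** Subtract an assumed confounding amount d (log-odds per SD of knowledge) from the coefficient of M, from 0 to the value at which the mediated effect is zero. Hold the estimated total effect fixed and say so. Report the mediated effect and the share at each d with bootstrap intervals. Do not benchmark d by the change between the unadjusted and demographic-adjusted models. The analysis shows how strong confounding would have to be; it does not remove it.

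The cost is a weaker claim about CRC knowledge, edits in three places and a small extra analysis. No new visit, survey item or video edit is needed.

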1 STUDY OBJECTIVES

1.4 Primary Objective

The Primary Objective of this study is to identify novel Latino-perceived barriers to participation in CCTs.

1.5 Secondary Objectives

1. Assess the impact that CRC educational videos in Spanish may have on participants' CRC knowledge.
2. Assess the potential relationship between an increase in health knowledge of a specific cancer via educational videos in Spanish and willingness to participate in CCTs.

2 INVESTIGATIONAL PLAN

2.1 Study Design

Type of Design: Single-arm intervention study

Brief Overview of Study Phases: Following completion of the Hispanic Masses at STM Church on Saturday and Sunday, attendees will be approached by members of our study team and CHWs. They will be screened for their eligibility to participate in our study through an Intake Form which they will be able to complete either in-person while they are at the Church, or through the project website. Those deemed eligible will be prompted to complete the RIS online, in-person, or via the phone. Those that complete the RIS and enroll in the study will be scheduled to come to STM Church on future *Study Days*. During *Study Day 1*, participants will complete the *CRC Knowledge Survey*, watch three CRC educational videos in Spanish and then complete the *Post Video CRC Knowledge Survey*. On *Study Day 2* (30 +/- 7 days after their participation in *Study Day 1*), participants will return to STM Church in order to complete the *30 Day Follow Up CRC Knowledge Survey*. Subsequently, on *Study Day 3*, 20 of the 60 participants will participate in a one-on-one qualitative interview aimed at identifying barriers preventing Latinos from participating in CCTs.

2.2 Study Duration, Enrollment and Number of Participants

Participant commitment will consist of at least two and a half hours over a 4-month period (two hours to take the *CRC Knowledge Survey*, watch the videos and take the *Post Video CRC Knowledge Survey* and thirty minutes to complete the *30 Day Follow Up CRC Knowledge Survey*). Participants willing to take part in a qualitative one-on-one interview will commit an additional hour, totaling three and a half hours over a 6-month period. The entire study is expected to last 12 months. We intend to enroll a total of 60 participants. However, in order to recruit the necessary 20 for the qualitative interview, we may need to enroll more than 60 since not everyone participating in *Study Days 1 and 2* will choose to participate in *Study Day 3*.

2.3 Study Population

Participants should:

- (1) Self-identify as Hispanic/Latino.
- (2) Be Spanish speakers.
- (3) Be 18 years or older.

Participants will be excluded if they:

- (1) Do not identify as Hispanic/Latino.
- (2) Are not Spanish speakers.
- (3) Are younger than 18 years.

3 STUDY PROCEDURES

3.1 Screening/Baseline Visit procedures

Interested participants will be asked to complete an Intake Form in Spanish which captures name and contact information as well as determines study eligibility as listed above. Those deemed eligible will be prompted to complete the RIS. In addition to in-person recruitment, interested participants will have the opportunity to complete the Intake Form using our study website, which will be readily accessible via a QR code found on the Study Flyer.

